## 2 Protocol Summary

Title:	Treating Opioid Patients' Pain and Sadness (TOPPS)
Population:	163 participants currently being treated with buprenorphine

Intervention:	Intervention: 12-week lifestyle psychoeducation about pain, depression, and opioid use; as well as values-based, behavioral activation to increase engagement in meaningful activities. Timing: 3-months Method: Randomized controlled trial
Objectives:	1) to determine whether the TOPPS intervention, compared to HE, results in less pain interference and pain severity over the 3-month treatment phase; 2) to determine whether TOPPS, compared to HE, results in less depressive symptoms over 3 months; 3) to determine whether TOPPS, compared to HE, results in sustained improvements in pain interferences, pain severity, depressive symptoms, and buprenorphine treatment retention (self-reported continuous treatment) over the 12 months of the study.
Design/Methodology:	163 participants who are currently being treated with buprenorphine and who endorse pain and depressive symptoms were randomized into the trial. Recruitment occurred from two primary care, office-based addiction treatment (OBAT) buprenorphine clinics, as well as through online advertisement. Following consent and the baseline interview, participants were randomized to one of two study arms: the TOPPS intervention or health education. The TOPPS intervention consists of 3 main components: 1) psychoeducation about pain, depression, opioid use, their interactions, and the role of avoidance; 2) coaching in how to be an informed, activated patient; and 3) values-based, behavioral activation, to increase engagement in meaningful activities. The intervention is a total of 6 phone-based sessions over 12 weeks with a Behavioral Health Specialist (BHS). The control arm (health education) involves six sessions led by the same BHS. The first health education session is titled "What to Eat." Participants then select five additional topics, one for each of the remaining sessions. Topics include, "What Not to Eat," "Colds, Germs, and Flu," "Preventing Cancer," "Diabetes," "Protecting your heart," "Getting a Good Night's Sleep," "Complementary and Alternative Medicine (CAM)," "Caffeine," and "Physical Activity." Follow-up interviews are conducted by trained Research Assistants (RAs) at 1, 2-, 3-, 6-, 9-, and 12-months (for participants enrolled prior to XX) post-enrollment.
Total Study Duration:	5 years

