## 5 Study Design

Eligible participants will be adult men and women currently receiving buprenorphine. Participants will be randomized to either *the TOPPS intervention* or a health education intervention (HE). We will provide both interventions over three months and follow participants for a total of 9 months in order to observe both short-term and longer-term effects of *the intervention*. Participants are recruited from two primary care, office-based addiction treatment (OBAT) buprenorphine clinics in New England: a large, university-affiliated, hospital-based clinic and a community health center's buprenorphine program. In October 2021, during the COVID-19 pandemic, recruitment was expanded to include targeted online advertisement primarily seen on social media sites, facilitated by BuildClinical LLC, a private software platform. After confirming study eligibility, the RA administers and documents informed consent within 14 days of the participant screening eligible. Prior to March of 2020, informed consent procedures

occurred in-person and took place on the same day as the participant's baseline visit. All onsite research activities were paused at the onset of COVID-19 pandemic. Remote research activities resumed in October of 2020. At that time, the study team transitioned all research activities to be conducted over the phone and via mail. Informed consent is collected via an e-consent form. Upon signing of the informed consent, a subsequent baseline interview is scheduled. Eligible participants are administered the assessment and are randomized to one of the two study arms upon completion of the interview. Randomization is stratified on three factors: study enrollment site, disability status, and currently taking an antidepressant medication using randomly permuted blocks. There is a 1:1 random allocation of the intervention between the study groups. Follow up interviews are conducted by trained RAs at 1-, 2-, 3-, 4-, 6-, 9-, and 12-months (for participants enrolled prior to October 2023) post-enrollment.

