## 15.3 Statistical Methods

We will present descriptive statistics. Random effects logistic regression will be used to determine if treatment condition, demographic characteristics, or baseline outcome measures predict study attrition. Any variables that significantly ( $p < .10$ ) predict study attrition will be included in multiple imputation models and as covariates in multivariate models testing the effects of intervention. Graphical methods will be used to evaluate the distributions of outcome variables, examine model residuals, describe change in outcomes over time, and guide the specification generalized linear mixed models testing intervention effects. A 2-tailed probability of Type I error  $< 0.05$  will be used for all null hypothesis tests. Missing data due to participant attrition and item non-response is inevitable. We will conduct intent-to-treat analysis using multiple imputation by chained equation (MICE) to generate fully populated data sets [20]. More specifically we will use the mi impute and mi estimate facilities in Stata 17 to generate and analyze the fully populated data files [21]. The number of imputed data sets will be determined by using the how many imputations procedure [22]. MICE is a flexible tool that allows imputing values for outcomes with a range of distributions (e.g., continuous, dichotomous, count, etc.). MICE assume data are missing at random (MAR) (e.g., missing is random conditional on variables in the imputation model). Variables used in the imputation models will include treatment assignment, all observed instances of the outcome being imputed, and any additional baseline variables found to significantly ( $p < .10$ ) predict subject attrition using mixed-effects logistic regression. Including baseline predictors of attrition supports the MAR assumption.

The BPI, the VAS pain severity scales (worst and average in last week), and the PHQ-9 will be administered at baseline and at all follow-up assessments. The effect of intervention on pain interference (BPI-I), pain severity, and depressive symptoms during the 3-month treatment phase will be evaluated in a generalized linear mixed model framework using the fully populated data sets generated by MICE. Models will include baseline pain and PHQ-9 depression measures as covariates. All available panel data will be included in the model to support the efficiency of estimation. Time specific estimates

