of treatment effects (e.g., the effect of treatment at 3-months) can be obtained by including the treatment by categorical (indicator variables) time interaction term. We plan to use the contrast and mimrgns post-estimation commands in Stata to recover relevant parameter estimates and test statistics. More specifically, a Wald  $\chi^2$ -test will be used to test the simple main effect of treatment at end of treatment. Additionally, we will generate graphs plotting the estimated average marginal means to facilitate substantive interpretation of results. Parallel methods will be used to evaluate the sustained effect of treatment post end-of-treatment (4-, 6-, 9-, and 12- months). Wald  $\chi^2$ -tests will again be used to test the simple main effects of treatment at post end-of-treatment assessments to determine if intervention effects are sustained over time.

The Cox proportional hazards model will be used to test the hypothesis that participants randomized to TOPPS will have higher buprenorphine treatment retention than persons randomized to HE. The outcome will be operationalized as self-reported continuous treatment since the prior interview at the time point assessed.

We will use Mplus 7 [23] to specify and estimate structural equation models (SEM) testing the hypothesis that decreased avoidance, and fear of pain mediate the relationship between intervention and pain interference and severity.

Additional baseline covariates will include ratings of pain severity, pain interference, and depression. As recommended by MacKinnon et al. [24], the statistical significance of the indirect effect will be assessed using bias-corrected bootstrapped standard errors. Significant indirect effects are consistent with the hypothesis that change in the purported mechanisms mediates the effect of intervention on outcome.

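### Site, disability status and antidepressant use stratify the randomisation but are not pre-specified in the outcome or imputation models of section 15.3; if they are prognostic, power is forgone

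*Combined protocol and SAP*

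**What the plan says.** Section 5 (Study Design) sets the randomisation: "Randomization is stratified on three factors: study enrollment site, disability status, and currently taking an antidepressant medication using randomly permuted blocks". Allocation is 1:1.

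Section 15.3 (Statistical Methods) then sets the models:

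- **Pain and PHQ-9 models:** "Models will include baseline pain and PHQ-9 depression measures as covariates". The only other terms given are treatment, categorical time and their interaction.
- **Retention:** "The Cox proportional hazards model will be used to test the hypothesis that participants randomized to TOPPS will have higher buprenorphine treatment retention". No covariates or strata are listed.
- **Attrition screen:** "Random effects logistic regression will be used to determine if treatment condition, demographic characteristics, or baseline outcome measures predict study attrition". Variables that reach p < .10 "will be included in multiple imputation models and as covariates in multivariate models testing the effects of intervention".
- **Imputation models:** "Variables used in the imputation models will include treatment assignment, all observed instances of the outcome being imputed, and any additional baseline variables" that predict attrition at the same threshold.

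On size, section 15.2 plans 125 per arm, 250 in all. The Protocol Summary reports that "163 participants who are currently being treated with buprenorphine and who endorse pain and depressive symptoms were randomized into the trial".

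**The concern.** Stratified blocks force the three factors to be nearly balanced between arms. That balance reduces the true variability of the treatment estimate if the factors predict the outcome. A model that leaves them out keeps their variance in its residual, so it reports a standard error that is too large. The test then rejects less than 5% of the time under the null, and the precision gained by stratifying is not used.

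The attrition screen does not close the gap. Its candidate list covers treatment arm, demographics and the baseline values of the outcomes. Disability status might count as demographic, but site and antidepressant use are not clearly on it. Even a screened factor enters only if the trial's own dropout data select it. Predicting dropout is a sound reason to put a variable in an imputation model, but it is a different property from predicting pain or PHQ-9.

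At stake is power, in a trial that randomised 163 against 250 planned. Validity is not: the linear estimate is not biased and type I error is not inflated. The Cox model is a separate case, because omitting prognostic factors there pulls the hazard ratio toward 1.

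**Working it through.** **Inputs from the documents.** Standardised difference 0.4, 99 analysed per arm, 80% power, 20% attrition, 125 recruited per arm (15.2); two-sided 5% tests (15.3); 163 randomised (Protocol Summary).

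**Assumed, because the documents do not give them.** R², the share of outcome variance that the three factors explain beyond baseline pain and PHQ-9: 0 to 20%. Strata: 2×2×2 = 8, or 3×2×2 = 12 if online recruits formed their own site level. Blocks of 4 or 6. Loss at random. The difference of 0.4 is scaled to the SD left after baseline adjustment.

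**The plan's own figure.** n = 2(1.96 + 0.842)²/0.4² = 98.1, so 99 per arm, and 100/0.8 = 125. Both reproduce at two-sided 5%.

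**Closed form, perfect balance.** Let SE = √(2/n) be the standard error that the model without the factors reports. The true one is SE·√(1−R²). Then:

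- type I error without the factors = 2Φ(−1.96/√(1−R²))
- power without = Φ((0.4/SE − 1.96)/√(1−R²))
- power with = Φ(0.4/(SE·√(1−R²)) − 1.96)

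For 163 randomised, n = 163 × 0.8/2 = 65.2 per arm, SE = 0.175 and 0.4/SE = 2.28. For 99 per arm, SE = 0.142 and 0.4/SE = 2.81.

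| R² | SE too large by | Type I error without | Power without / with, 65.2 per arm | Power without / with, 99 per arm |
|---|---|---|---|---|
| 2% | 1% | 4.8% | 62.8 / 63.6% | 80.6 / 81.1% |
| 5% | 2.6% | 4.4% | 63.0 / 64.9% | 81.0 / 82.3% |
| 10% | 5.4% | 3.9% | 63.4 / 67.3% | 81.6 / 84.3% |
| 20% | 11.8% | 2.8% | 64.1 / 72.4% | 83.0 / 88.2% |

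**Simulation with real blocks and 20% loss.** Stratified permuted blocks, 163 randomised, a baseline-adjusted linear model at one time point, 8,000 runs per setting. Incomplete blocks and dropout weaken the balance, so the excess in the standard error is smaller than in the table.

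| R² | Change in power with the factors (points) | Type I error without | SE too large by |
|---|---|---|---|
| 0 | −0.9 to −0.1 | – | – |
| 2% | +0.4 to +0.7 | – | – |
| 5% | +1.6 to +1.8 | 4.4–4.5% | 1–2% |
| 10% | +3.2 to +4.0 | 3.9–4.4% | 3–5% |
| 20% | +7.9 to +8.9 | 3.4–3.6% | 7–9% |

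Repeat runs with 12 strata and blocks of 4 gave gains of about 1–1.5, 3.4–4 and 8–9 points at shares of 5%, 10% and 20%. Type I error without the factors was 4.3–4.9%, 3.6–4.8% and 3.0–3.6%. At 5% the conservatism is therefore hard to separate from simulation error. At 20% it is clear.

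**With multiple imputation.** Months 1–3, monotone loss of 10%, 15% and 20%, 15 imputations, Rubin's rules, a month-3 model and 1,800 runs per share. Monte Carlo error is about 1.1 points for power and 0.5 for type I error.

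| R² | Power as planned | Factors in outcome model only | Factors in both models | Type I error, planned / both |
|---|---|---|---|---|
| 5% | 63% | 64% | 65% | 4.5 / 4.7% |
| 10% | 64% | 67% | 66% | 3.9 / 4.7% |
| 20% | 64% | 68% | 72% | 2.9 / 5.1% |

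**Cox model.** 163 participants, 1,500 runs per setting, each factor assumed to have a hazard ratio of 1.5 or 2.0. A true treatment hazard ratio of 0.50 is estimated as 0.51 or 0.53 unadjusted and 0.50 adjusted. Further runs place this shift at about half of participants having an event. At about 15% events there is little shift.

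**The case against.** The strongest reply is that any harm is conditional and on the safe side. The models already adjust for baseline pain and PHQ-9, and disability and antidepressant use may act mostly through those scores. Nothing in the documents supports a 20% residual share, and at 2–5% the gain is under 2 points. This stands as a limit on size. It does not defend leaving the factors to a dropout screen.

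The imputation half is thinly supported. Putting the factors in the imputation model as well as the outcome model makes a visible difference only at a 20% share. That also stands. The reason to do it is that an imputation model should contain every analysis-model variable, and it costs nothing.

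The shortfall from 250 to 163 is a much larger loss of power than adjustment can repair. By the closed form, adjustment gains 1.4, 2.7 and 5.2 points at 99 per arm against 1.9, 3.9 and 8.2 at 65.2. So it matters more at the realised size, but it does not restore the planned power.

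The Cox shift depends on an event rate that the documents do not give. It is small beside a log hazard ratio standard error of 0.21–0.45, and much of it is the difference between marginal and conditional hazard ratios. That is why it is a secondary element here.

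The imputation sentence admits further baseline variables, so the candidate list may be wider than it first reads. Entry still depends on p < .10 for attrition, so this is not pre-specification.

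Finally, the full mixed model with treatment-by-time was not simulated. The figures come from single-time-point models, with and without imputation.

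**Conclusion.** The concern holds. Section 5 builds three factors into the randomisation, and section 15.3 guarantees none of them a place in any model. The direction is certain if the factors are prognostic beyond baseline pain and PHQ-9: conservative tests and unused power. The size rests on an assumed variance share. At 163 randomised with 20% loss it is under 1 point of power at 2%, about 2 points at 5%, 3–4 at 10% and 8–9 at 20%. At the planned 99 per arm, power without the factors stays at 80–83%, so the sample-size statement is intact. This should be corrected, but it does not invalidate the analysis.

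**What to change.** In section 15.3:

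1. Name site, disability status and antidepressant use as fixed covariates in the pain and PHQ-9 models, whatever the attrition screen finds. Code site, including online recruits, as it was at randomisation.
2. Put the three factors, with baseline pain and baseline PHQ-9, in every imputation model. As written, baseline PHQ-9 is not guaranteed a place in the pain imputation model although it is an analysis covariate.
3. Adjust for the factors in the Cox retention model or stratify on them, to reflect the design and limit attenuation of the hazard ratio.
4. Keep the attrition screen as an addition to the imputation model, not as the route by which stratification factors enter.
5. Date the change before outcomes are examined by arm. If that has already happened, keep the planned model as primary and report the adjusted one as a labelled sensitivity analysis.

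The cost is a few sentences and three or four degrees of freedom, since the factors are known for everyone at randomisation. If they explain nothing, the linear models lose 0.1–0.9 point of power. A stratified Cox model cost at most about 2–3 points in simulation, so covariate adjustment is the cheaper choice if some strata are small.

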## 4 Objectives

### 4.1 Study Objectives

The described study is a randomized clinical trial of the Treating Opioid Use, Persistent Pain, and Sadness (TOPPS) intervention compared to health education (HE) contact-control condition among

persons receiving buprenorphine for opioid use disorder. The study objectives are as follows: 1) to determine whether the TOPPS intervention, compared to HE, results in less pain interference and pain severity over the 3-month treatment phase; 2) to determine whether TOPPS, compared to HE, results in less depressive symptoms over 3 months; 3) to determine whether TOPPS, compared to HE, results in sustained improvements in pain interferences, pain severity, depressive symptoms, and buprenorphine treatment retention (self-reported continuous treatment) over the 12 months of the study. Mechanisms by which TOPPS may reduce pain interference will also be examined, including 1) (increased) activities of engagement; 2) (decreased) avoidance of meaningful life activities; and 3) (decreased) fear of pain.

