### 4.2.2 Secondary Outcome Measures

- **Depression**

The PHQ-9 (Patient Health Questionnaire-9) will be used to measure depression severity and suicidality. It is a commonly used clinical interview that yields a depression severity score between 0 and 27.

- **Buprenorphine treatment retention**

Buprenorphine treatment retention will be measured via chart review and participant self-report.

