## 7.2 Subject Exclusion Criteria

An individual who meets any of the following criteria will be excluded from participation in this study:

- Expected surgery in the next 3 months

- Pain thought to be due to cancer
- Greater than or equal to 10 days of cocaine/crack/methamphetamine use in the past month
- Current mania or past year psychosis as determined via SCID (Strutured Clinical Interview for DSM) Modules A and B/C
- Lifetime diagnosis of schizophrenia or other chronic psychotic condition as determined by the study PI
- Planning to stop using buprenorphine in the next 6 months
- Headache/migraine is the only reported site of pain
- Pregnancy or planned pregnancy in the next 6 months
- Greater than 8 homeless nights in the past month
- Suicide ideation or behavior requiring immediate attention
- Not able to complete interviews in English
- Unable to provide names and contact information for at least two verifiable locator persons who will know where to find them in the future
- Greater than or equal to 45 days without a phone in the past 3 months/no reliable access to phone
- REMOTE ONLY: Does not have internet access or mailing address
- IF PASSIVE RECRUITMENT: Cannot confirm active buprenorphine prescription

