### **Baseline and Follow-Up Assessments:**

The baseline visit will take place at BMC (Boston Medical Center) or SSTAR if possible, but may also be conducted by telephone. At consent/baseline, research staff will collect participants' contact information, including phone number(s), mailing address, and e-mail address if applicable. Staff will also collect the phone numbers for two alternate contacts that they may call if unable to reach the participant. Research staff will keep in regular contact with participants by phone or by text message,

and participants will be encouraged to contact the study team if they change their contact information. If participants report that they plan to enter a temporary residence, shelter, or facility, they will be asked to fill out a form authorizing the facility to release their admission status and/or contact information to study staff. If remote, this form can be sent electronically (REDCap/Docusign). If this is not possible, we will wait to complete this form until assessments can occur in person. If a participant becomes incarcerated during study participation, research staff will not complete assessments with them while incarcerated but will monitor release date to re-engage the participant upon release. Participants will be compensated for each assessment and FitBit Inspire return and we will attempt to contact participants for all assessments regardless of whether they remain in the assigned treatment (see Table 1). Compensation can include Visa® gift cards or electronic gift cards. We may also cover local transportation costs and offer offsite or phone assessments to increase convenience for participants.

The baseline interview is administered by trained RAs and takes approximately two hours to complete. A list of assessment measures is included in the Appendix. Participants are mailed or emailed assessment scales prior to the scheduled call. Participants' eligibility is reassessed at this time, and if they are found to be no longer eligible, they are compensated and thanked for their time. Eligible participants are administered the assessment and are randomized upon completion of the interview.

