## 14.2 Study Documentation, Source Data, and Case Report Forms (CRFs)

Data sources in the study include pre-screening data collected via BuildClinical, the phone screening data, baseline, 1-, 2-, 3-, 5-, 6-, 9- and 12-month assessment data to be collected via phone or in-person and input into REDCap by study staff, medical record data, and, audio-recordings.

Screening information collected via BuildClinical will be housed securely in BuildClinical's online platform. Screening information on potentially eligible participants collected by BU study staff will be housed securely in REDCap.

The phone screen and study baseline and follow-up interview data will be collected verbally from the participant to study staff over the phone, and directly entered by research staff into REDCap case report forms, and stored electronically in REDCap. Information collected during the phone screening is collected to determine eligibility for the study. Research interviews will collect information on demographic variables, health and medical status, symptoms of anxiety and depression, pain, recent medical appointments, current medications, knowledge of opioids, pain treatments, physical activity, substance use, psychosocial functioning, experience of discrimination, satisfaction with the intervention, and more. Data collected at the follow up time points are to understand change over time, especially after the intervention period.

RAs conducted medical chart reviews from participants who were recruited from the two primary care, office-based addiction treatment (OBAT) buprenorphine clinics in New England to collect data on buprenorphine retention at 6- and 12-months post-enrollment.

Corrections on data collection forms: If any entry error has been made to hardcopy data collection forms, to correct such an error, a single straight line will be drawn through the incorrect entry and the correct data will be entered above it. All such changes will be initialed and dated. There will be no erasures or white-out on CRFs. For clarification of illegible or uncertain entries, the clarification will be printed above the item, then initialed and dated.

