## 15.2 Sample Size Determination

We plan to recruit 125 subjects to each study condition. Based on an attrition rate of 20% we anticipate having approximately 100 participants per condition available for analysis. Our primary power calculations are based on Aim 1. Based on the literature [17-19], we determined that a minimally significant difference between treatment groups on outcomes would be a standardized mean difference (SMD) of at least 0.4 at 3 months. Assuming  $\alpha/2 = 0.05$ , we need 99 subjects per arm to detect an SMD of 0.4 with  $1-\beta = 0.8$ . Thus, the proposed design has sufficient power to detect small-moderate effects for Aims 1 and 2.

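### The 6- and 12-month buprenorphine chart reviews have no role in the retention analysis, and the plan does not say how loss to interview is handled

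*Combined protocol and SAP*

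**What the plan says.** Objective 3 (Sections 2 and 4.1) concerns "buprenorphine treatment retention (self-reported continuous treatment) over the 12 months of the study". Section 4.2.2 is wider: "Buprenorphine treatment retention will be measured via chart review and participant self-report". Section 14.2 reports that research assistants reviewed the charts of participants recruited from the two clinics "to collect data on buprenorphine retention at 6- and 12-months post-enrollment". Online recruits are not covered.

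Section 15.3 describes one retention analysis: "The Cox proportional hazards model will be used to test the hypothesis that participants randomized to TOPPS will have higher buprenorphine treatment retention". The outcome is then defined: "The outcome will be operationalized as self-reported continuous treatment since the prior interview at the time point assessed". Charts are not mentioned in Section 15.3.

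Section 15.3 announces an intent-to-treat analysis by chained-equation imputation and ties it explicitly to the pain and depression models. It does not say whether the imputed data also feed the Cox model. No censoring rule is given, either for people lost to interview or for those whose last scheduled interview is month 9 (Section 5 limits the 12-month interview to people enrolled before October 2023).

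**The concern.** A self-reported stop can be seen only if the person comes back and reports it. People who stop buprenorphine may also be the ones who drop out of interviews, so censoring may be related to the event being counted. For clinic recruits the trial holds a second source that does not depend on the interview, but the plan does not use it.

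Three things are at stake: the number of events, the retention percentages and, if loss after stopping differs between arms, the hazard ratio. Retention is a secondary outcome for which Section 15.2 claims no power. The primary pain outcomes are not touched.

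**Working it through.** **1. The plan's own figure.** Section 15.2 uses a standardised difference of 0.4 and power 0.80. At two-sided 0.05, n per arm = 2(1.96 + 0.8416)² / 0.4² = 98.1, rounded up to 99, which matches. Allowing for 20% attrition, 100 / 0.8 = 125 per arm also matches. Both figures serve Aim 1. The documents give no retention rate, hazard ratio, event count or clinic share, so everything from step 3 on rests on assumptions.

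**2. One lost participant followed through the plan.** Suppose a clinic recruit stops between months 4 and 6 and gives no interview after month 4.
- Cox model, usual handling: censored at month 4, no event, out of the risk set afterwards.
- Attrition regression: its predictors are treatment condition, demographics and baseline outcome measures. It cannot register that stopping caused the loss.
- Imputation, if it covers retention: the listed variables are treatment, observed values of the outcome and baseline predictors of attrition. Chart status is not among them.
- Chart review: could show the stop by month 6, but no analysis reads it.

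**3. How many stops charts could recover.** Inputs are 163 randomised (Section 2) and 20% attrition (Section 15.2, time point not stated, read here as loss by month 12). Lost = 163 × 0.20 = 32.6. Assume 25–75% of these are clinic recruits and 25–75% of those have stopped:
- low: 32.6 × 0.25 × 0.25 = 2.0
- middle: 32.6 × 0.5 × 0.5 = 8.2
- high: 32.6 × 0.75 × 0.75 = 18.3

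Schoenfeld power with equal arms is Φ(½√D·|ln HR| − 1.96). If 20% of those observed report a stop, D = 163 × 0.8 × 0.2 = 26.1. At an assumed hazard ratio of 0.6, power is 26%. Adding 2.0, 8.2 or 18.3 events gives 27%, 32% or 40%.

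**4. Simulation of the comparison.** Settings: 82 v 81 participants; exponential time to stopping; interviews at months 1, 2, 3, 4, 6, 9 and 12; Efron ties; 2000 replicates. Assumed loss per interview is 1–2% on treatment and 8–30% off treatment, and is permanent. Half are assumed to be clinic recruits, with charts consulted only for those lost to interview.

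| Assumed truth and loss | Self-report only | With charts |
|---|---|---|
| HR 0.6, 40% of HE stop (54 true stops), equal loss 18–20% | 44–45 events; HE retention 63–64% (true 60%); power 38–40%; HR 0.58–0.60 | 49–50 events; 61–62%; power 41–43% |
| HR 0.6, 20% of HE stop (26 true stops), equal loss | 21 events | 23–24 events |
| HR 1.0, off-treatment loss HE 15% v TOPPS 8% | HR 1.07–1.09, rejection 5–6%; reversed 0.92–0.93 | 1.03–1.05; reversed 0.96–0.97 |
| HR 1.0, HE 25% v TOPPS 8% | HR 1.21–1.23, rejection 9–10%; reversed 0.82, 11% | 1.09–1.11; reversed 0.91; rejection 5–7% |

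In the equal-loss cases, charts would be consulted for about 9–12 people and would reclassify 3–5. In the 25% v 8% case, the self-report hazard ratio falls to 1.14 if half of participants' misses are permanent. It falls to 1.06 if misses are independent by visit and the break is reported on return.

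**5. A harsher check.** In a separate simulation, 30% stop by month 12, the true hazard ratio is 1, and 60% of HE stops but 30% of TOPPS stops are hidden. The hazard ratio reads 1.69, and 1.20 with charts on half. Reversed, it reads 0.59 and 0.82. With half of stops hidden in both arms it stays at about 1.00.

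**The case against.** The strongest reply is that self-report is a declared choice, made consistently in Sections 2, 4.1 and 15.3, and the only source collected alike for clinic and online recruits. That stands, and it is why self-report should stay the main analysis.

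The plan also works to limit loss. Section 12 says "we will attempt to contact participants for all assessments regardless of whether they remain in the assigned treatment", locator contacts are required, payment rises over time, and each session asks about buprenorphine adherence. Someone who returns after a gap can report a break. Section 7.2 excludes anyone "Planning to stop using buprenorphine in the next 6 months", which may keep stops few. Permanent loss is therefore the worst case.

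The planned attrition regression does test arm. A simple two-proportion version at p < .10 would flag the 25% v 8% case in 62–65% of trials and the 15% v 8% case in 13–28%. A flag would not correct the bias, since treatment is already in the model.

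A reader might infer more than the documents support:
- **That lost participants are counted as retained to month 12.** No passage says so. Usual Cox handling censors them at the last interview, and if imputation covers retention they could receive an imputed status. The handling is simply not stated.
- **That retention is overstated.** This holds only if loss depends on stopping. The simulations assume that dependence, and the documents give no rates.
- **That the hazard ratio is biased.** This also needs loss that differs by arm, for which the documents give no evidence. In the mild case the shift is small against sampling error: with 45 events the standard error of the log hazard ratio is about 2/√45 = 0.30, and ln 1.09 = 0.086.

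**Conclusion.** The point holds as a minor one. Chart review is named as a retention measure and reported as done for clinic recruits, yet the analysis section gives it no use. The treatment of loss to interview, and whether imputation reaches the Cox model, are both unstated. A stop followed by permanent loss would go unrecorded under usual handling, and nothing written in Section 15.3 would recover it.

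On the assumed rates, equal loss costs some events and about 3–4 points of apparent HE retention, with the hazard ratio essentially unchanged. Mildly unequal loss has little effect. The effect is material only when loss is strongly unequal between arms and permanent. These sizes rest on assumed stopping rates, loss rates and clinic share, and on reading "Based on an attrition rate of 20% we anticipate having approximately 100 participants per condition available for analysis" as loss by month 12.

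**What to change.** Keep the self-report Cox model as the main analysis. Before retention is compared by arm, add to Section 15.3:

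1. A supporting analysis of 6- and 12-month chart retention in all clinic recruits in both arms, with rules for conflict between chart and self-report and for transfers of care. Using charts only for those lost would mix ascertainment methods and would never compare the two sources. Report the number of clinic recruits by arm.
2. Use of chart status to ascertain discontinuation in clinic recruits lost to interview.
3. A sensitivity analysis that treats unexplained loss as discontinuation, varied by arm and read as a tipping point.
4. The censoring rule, including for people whose last interview is month 9 (for example, censor at month 9 and use only their 6-month chart), and whether imputation feeds the Cox model.
5. Consistent wording of the retention measure in Sections 4.1, 4.2.2 and 15.3.

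The cost is SAP wording and modest programming on data the protocol reports as collected. The main endpoint does not change.

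The repair is partial. Charts do not cover online recruits: at a quarter clinic share, the 25% v 8% case falls only from 1.23 to 1.17. Stop dates may be coarse, and a transfer may be misread as a stop. If 10–20% of lost clinic recruits transferred and were misread, the simulated chart hazard ratio moved by at most 0.01. That figure applies to item 2 only, not to the all-recruit analysis.

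The sensitivity analysis is blunt. Counting all loss as discontinuation dilutes a true 0.6 to 0.65–0.69 (0.75 if only 20% of HE stop). Applied to one arm only, it gives 0.42–0.45 (HE) or 0.86–0.98 (TOPPS), widening to 0.30 and 1.47 if only 20% stop.
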